Serology (HBsAg, HCVAb, antiHIV 1 and 2)	X																			
Urine Drug and Alcohol Screen 	X	X																		
FSH (postmenopausal females only)	X																			
Pregnancy Test (Females Only) 	X	X																	X	X
Clinical Laboratory Test 	X	X	X			X				X							X		X	X
12-lead ECG 	X	X	X	X	X	X	X	X	X	X	X X	X	X	X	X	X			X	X
Vital Signs 	X	X	X	X	X	X	X	X	X	X	X	X	X	X	X	X	X		X	X
Eligibility Check	X	X																		
Randomization		X																		
Study Drug Administration				X	X	X	X	X	X	X	X	X	X	X	X	X	X			
Blood Sampling for PK 			X	X	X					X				X	X	X	X	X	X	
Expired CO Level 	X	X	X	X	X	X	X	X	X	X	X	X	X	X	X	X	X			
Blood Sampling for Cotinine 			X							X							X			
Smoking Log		X		X	X	X	X	X	X	X	X	X	X	X	X	X	X	X		
FTCD	X																			

Altasciences Project Number: CNO-P5-319

			Assessment Period																	
Visit 	Screening	Pre	etreatment	nt Treatment											Followup/ End of Study 					
Study Day	-28 to -2	-1	1 (Predose)	1	2	3	4	5	6	7	8	9	10	11	12	13	14	15	16	21±1
Smoking TLFB	X	X																		
MNWS		X		X	X	X	X	X	X	X	X	X	X	X	X	X	X			
QSU-Brief		X		X	X	X	X	X	X	X	X	X	X	X	X	X	X			
C-SSRS Questionnaire 	X	X															X			X
M.I.N.I.	X																			
Previous and Concomitant Medication	X	X	X	X	X	X	X	X	X	X	X	X	X	X	X	X	X	X	X	X
Adverse Event Monitoring		X	X	X	X	X	X	X	X	X	X	X	X	X	X	X	X	X	X	X

Abbreviations: BMI = body mass index; C-SSRS = Columbia-Suicide Severity Rating Scale; CO = carbon monoxide; ECG = electrocardiogram; EOS = end of study; FSH = follicle-stimulating hormone; FTCD = Fagerström Test for Cigarette Dependence; HBsAg = hepatitis B surface antigen; HCVAb = hepatitis C virus antibody; HIV = human immunodeficiency virus; MAD = multiple ascending dose; M.I.N.I. = Mini International Neuropsychiatric Interview; MNWS = Modified Minnesota Nicotine Withdrawal Scale; PK = pharmacokinetic; QSU-Brief = Questionnaire on Smoking Urges - Brief version; TLFB = Smoking Time-Line Follow-back

- The timing, type, and number of safety, and PK assessments may be updated depending on emerging safety and PK data.
- 2 Subjects who discontinue the study early should complete the EOS procedures.
- 3 An abbreviated physical examination may be performed at the Investigator's discretion upon admission or discharge from the clinical site.
- 4 Weight only.
- 5 See APPENDIX 6 for details.

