## For Cohorts A1, A2, A4, and A5:

- Subjects will be confined to the CRU from at least 10 hours prior to drug administration until approximately 48 hours after study drug administration. Subjects will therefore be confined for 4 days and 3 nights (Day -1 to Day 3). However, they may be advised to stay longer at the CRU for safety reasons, if judged necessary by an Investigator.
- Subjects will return for a follow-up visit approximately 5 days after the last PK blood sample/discharge (Day 8±1).
- Total study duration: up to 38 days (including Screening)

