All relevant safety and available plasma PK data will be reviewed by the DSMB before any dose escalation. The dose levels proposed for MAD cohorts may be adjusted during the course of the study based on preliminary safety and PK data. The dosing frequency may also be changed from once daily to twice daily, without changing the total daily dose outlined in the protocol.

The MAD phase will have a maximum of 4 cohorts. The number of cohorts may be changed at the discretion of the Sponsor depending on the emerging safety and PK data from the previous cohorts. The increase from one dose level to the next dose level will not be more than 3-fold. A MAD daily dose level cannot be higher than the highest dose level tested in SAD.

Subjects will be confined to the CRU from at least 10 hours prior to drug administration until approximately 48 hours after last study drug administration. Subjects will therefore be confined for 17 days and 16 nights (Day -1 to Day 16).

Subjects will return for a follow-up visit approximately 5 days after the last PK blood sample/discharge (Day 21±1).

The schedule of activities of the MAD Phase of the study is described in Table 2.

Altasciences Project Number: CNO-P5-319

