## 3.5.2. Cohort Stopping Rules

If any of the following safety concerns are observed, dosing of all subjects at the given dose level or higher will be suspended/halted and all available data will be evaluated by the DSMB.

Dose continuation (remaining subjects within a cohort or remaining dosing for a subject) or escalation should not proceed for any of, but not limited to, the following reasons:

- If one SBP-9330-related SAE occurs in a cohort
- Severe AE at least possibly related to SBP-9330 in two or more subjects in the same cohort\*
- Other findings that, at the discretion of the DSMB or Sponsor, indicate further dosing should be stopped

\* Prior to suspending the cohort, if severe AEs are reported in two or more subjects at a given dose level, consideration should be given to the treatment assignment (SBP-9330 or placebo). After causality assessment, the Investigator (or designee) should open the individual randomization code to verify the treatment received. Dosing at the given dose level may continue if only one subject received SBP-9330 and the other(s) received the placebo.

Subjects experiencing severe AEs will be followed up with serial measurements of the related clinical parameter(s), as per medical judgment, until resolution, stabilization, or until the subject is lost to follow-up.

Dose escalation will be discussed during the DSMB meeting and may be stopped depending on Principal Investigator's or Sponsor's decision, based on but not limited to the following:

- New clinically significant abnormalities in physical examination, 12-lead ECG, or vital signs in two or more subjects
- Overall pattern of clinical changes or symptoms that may have appeared minor in terms of an individual AE or subject, but which collectively present a safety concern
- Clinically significant changes in organ-specific laboratory parameters (e.g., liver function enzymes in one or more subjects)
- Pattern of laboratory changes (e.g., a consistent increase or decrease in two or more subjects or within or across dosing cohorts) that might indicate an overall safety concern

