#### 4.3.2. After First Treatment Administration

Subjects may, at any time, voluntarily withdraw from the study or be removed from the study at the discretion of an Investigator or Sponsor. An Investigator may withdraw a subject at any time if it is determined that continuing the study would result in a significant safety risk to the subject or if their behavior is deleterious to the study environment.

If such withdrawal occurs, or if the subject fails to return for visits, an Investigator should determine the primary reason for a subject's premature withdrawal from the study and record the reason in the subject's study documents.

An Investigator may remove a subject from the study on the recommendation of the PK facility and/or Sponsor due to an unanticipated event that could result in an inadequately characterized PK profile, such as a missed blood draw, an AE, meal deviation or concomitant medication intake.

Attempts should be made to have such subjects complete the EOS/Follow-up assessments. The EOS/Follow-up assessments should be performed as soon as possible after the last study treatment administration.

The blind may be broken only in emergency situations, where knowledge of the treatment that the subject received is necessary for safety management (Section 5.2.4).

Details of reasons for removal of subjects will be recorded, reported to the Sponsor and documented in the clinical study report.

For subjects lost to follow-up (i.e., those subjects whose status is unclear because they fail to appear for study visits without stating an intention to withdraw), an investigator should show "due diligence" by documenting in the source documents steps taken to contact the subject, e.g., dates of telephone calls, registered letters, etc.

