## 7.4. Adverse Event Monitoring

For the purposes of this study, the monitoring period for AEs extends from the pretrial evaluation until the Follow-up Visit. From Screening to the first dose of the study, AEs will be recorded as screening events or as part of the medical history, as applicable. AEs occurring after initiation of study drug will be indicated as TEAEs in the clinical study report.

Altasciences Project Number: CNO-P5-319

Subjects will be questioned on their health status at the beginning of each study period and before each departure from the CRU. Open-ended questions will be asked.

During the study, all AEs spontaneously reported by the subject, observed by the clinical staff or elicited by general questioning will be recorded for all subjects and reported in the CRF.

If necessary, every effort will be made to obtain an adequate follow-up of the subjects. Should any subject choose to withdraw from the study, they will be advised of the safety precautions to be taken.

Any AE which remains unresolved as of the last visit will require an evaluation and follow-up until the AE has been resolved or a reasonable explanation for its persistence found, or is deemed mild and safely resolving.

In the case of AEs deemed related to the Investigational Product, every effort will be made to determine the final outcome.

It is an investigator's responsibility to ensure that subjects experiencing AEs receive appropriate follow-up treatment where required, and that every action is well documented.

Classification of AEs will be performed by System Organ Class (SOC) and Preferred Term (PT) using the Medical Dictionary for Regulatory Activities (MedDRA), version 23.0 or higher.

Concomitant medications will be coded using the World Health Organization drug dictionary (WHO-DDE March 2019 or later).

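### For subjects withdrawn after dosing, the EOS/Follow-up visit has no minimum post-dose interval, and collection of new adverse events ends at that visit; completers are observed for 7 days after the last dose

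*Protocol*

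**What the plan says.** - **Withdrawn subjects.** Protocol Section 4.3.2 covers withdrawal after first dosing for any reason. It says "Attempts should be made to have such subjects complete the EOS/Follow-up assessments", and then "The EOS/Follow-up assessments should be performed as soon as possible after the last study treatment administration". The clock is the last dose. No day, minimum or window is given.
- **Schedules of activities.** The footnotes to Tables 1 to 3 on early discontinuation (footnote 3 in Table 1, footnote 2 in Tables 2 and 3) say "Subjects who discontinue the study early should complete the EOS procedures". In Tables 2 and 3 they add no timing. Section 3.3 makes these procedures a requirement for early terminations, also without timing.
- **End of event collection.** Section 7.4 says "the monitoring period for AEs extends from the pretrial evaluation until the Follow-up Visit". The endpoint is a visit, not a fixed time after dosing.
- **Completers.** Part A single-dose cohorts (Section 3.3.1): "Subjects will return for a follow-up visit approximately 5 days after the last PK blood sample/discharge (Day 8±1"). Part B (Section 3.3.2): "Subjects will return for a follow-up visit approximately 5 days after the last PK blood sample/discharge (Day 21±1"). Section 3.3.3 gives the same day for Part C.
- **Events already under way.** Section 7.4 says "Any AE which remains unresolved as of the last visit will require an evaluation and follow-up until the AE has been resolved", with a reasonable explanation of persistence, or a mild and safely resolving course, as the alternatives. Section 3.5.2 adds "Subjects experiencing severe AEs will be followed up with serial measurements of the related clinical parameter(s), as per medical judgment, until resolution, stabilization", or loss to follow-up.
- **Analysis.** SAP Section 8 (Table 8) reports the number and percentage of subjects with TEAEs. SAP Section 8.1 treats every event reported after exposure as treatment-emergent, with no post-dose cut-off and no adjustment for length of observation.

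**The concern.** Because Section 7.4 ends monitoring at a visit, and Section 4.3.2 brings that visit forward for anyone withdrawn, the two rules together shorten the period in which new events are sought. The same visit carries the last scheduled laboratory tests, ECG, vital signs and C-SSRS, so those are brought forward too. A completer in Parts B and C has laboratory tests on Day 16 and Day 21±1, which is 2 and 7 days after the last dose. After an early EOS visit, nothing later is scheduled for a withdrawn subject.

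Adverse-event incidence and changes in these measurements are the primary endpoints (Section 2). SBP-9330 has not been given to humans before (Section 1.2.3), so the documents offer no human half-life or event-timing data to show that a shorter window would be enough. A withdrawn subject still counts in full in the denominator of a TEAE percentage, however briefly that subject was observed.

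**Working it through.** **1. Reproduce the completers' visit day.** Inputs: last dose on Day 1 (Part A, single dose) or Day 14 (Parts B and C); last PK sample and discharge about 48 hours later; follow-up about 5 days after that.

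- Part A: 1 + 2 + 5 = Day 8, as stated.
- Parts B and C: 14 + 2 + 5 = Day 21, as stated.

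**2. Completers' observation after the last dose** = follow-up day minus last dose day.

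- Part A: 8 − 1 = 7 days; with the ±1 day window, 6 to 8.
- Parts B and C: 21 − 14 = 7 days; with the window, 6 to 8.

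**3. Withdrawn subjects.** The interval *w* is not in the documents. The text permits the same day (*w* = 0) and sets no upper limit. Share of the completers' window = *w* / 7:

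| Assumed *w* (days) | Share of 7 days |
|---|---|
| 0 | 0% |
| 1 | 1/7 = 14% |
| 2 | 2/7 = 29% |
| 5 | 5/7 = 71% |

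At *w* = 1 the share runs from 1/8 = 12.5% to 1/6 = 16.7% across the completers' 8- to 6-day range.

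Example (hypothetical): a Part B subject whose last dose is on Day 5 could have the EOS visit on Day 5 or 6. The completers' interval would place it on Day 5 + 7 = Day 12 (Day 11 to 13).

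**4. Chance of seeing a new event (illustration).** Assume a constant event rate, with 30% of subjects having a new event within 7 days. The rate is −ln(1 − 0.30)/7 = 0.051 per day. The chance of seeing one within *w* days is 1 − exp(−0.051*w*): about 5% for 1 day and about 10% for 2 days. Neither the 30% nor the constant rate comes from the documents.

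**5. Effect of one missed subject on a full cohort's active-arm percentage.**

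- Part A, 6 active: 1/6 = 16.7 percentage points.
- Parts B and C, 8 active: 1/8 = 12.5 percentage points.

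Table 8 counts subjects, not events. The shift therefore arises only if the subject is not already counted in the category concerned: any TEAE, a given preferred term, a severity grade or a relatedness class. For a subject who already had a TEAE, a later one adds 0 points to overall TEAE incidence.

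**6. Where it applies.**

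- Parts B and C: dosing runs for 14 days, so a subject can leave well before Day 14.
- Cohort A3: a subject can leave after the Period 1 dose. Table 1, footnote 3 places this cohort's follow-up in Period 2, so Section 4.3.2 is the only timing rule for such a subject.
- Cohorts A1, A2, A4 and A5: there is one dose, and the same footnote says these subjects should return on Day 8±1. It can be read as keeping that day for early discontinuations too, so the short window is doubtful there.

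**The case against.** A reader might infer that subjects who stop for an adverse event get about one day of observation, after which their follow-up ends. The documents do not support this, for four reasons.

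- No day count is given; one day is only one reading of Section 4.3.2.
- The event that led to stopping is still followed. Section 7.4 continues past the last visit for unresolved events and asks for every effort to establish the outcome of related ones. Section 3.5.2 requires serial measurements for severe events.
- A confirmed drug-related moderate or severe event first leads to a held dose and a joint review (Section 3.5.1), which is not study withdrawal. Section 4.3.2 applies to all withdrawals, whatever the reason.
- A subject who stopped for a TEAE is already in the overall TEAE count.

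A reader might also infer that escalation decisions rest on 7 days of data for completers and far less for withdrawals. The DSMB reviews safety data up to discharge (Section 3.2), about 48 hours after the last dose, so completers' follow-up visits are not part of that minimum either. Delayed events in earlier cohorts are to be weighed (Section 3.5), but the 7-day contrast does not describe the data required for escalation. Nor do the documents say why subjects will withdraw; the 6:2 and 8:2 ratios describe allocation only.

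Two further safeguards are real but limited. Section 6.1 allows extra safety assessments at the Investigator's discretion, and Section 7.4 promises adequate follow-up if necessary; neither sets an interval. The SAP has no post-dose cut-off, so a late event that reached the database would be counted, but nobody is scheduled to ask for it.

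These points narrow the concern. They do not supply a rule for new-onset events or late measurements after an early EOS visit.

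**Conclusion.** The concern holds in a limited form. For subjects withdrawn after dosing, mainly in Parts B and C and Cohort A3, the protocol sets no minimum observation after the last dose and ends new-event collection at a visit it asks to be held early. Completers get 7 days (6 to 8). The shortfall cannot be fixed from the documents; the 0% to 71% range rests on assumed intervals of 0 to 5 days.

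What can be lost is new or delayed events and late scheduled laboratory, ECG, vital-sign and C-SSRS results. Follow-up of events already open, or severe, is not lost. The 1/6 and 1/8 shifts are the most one missed subject can add to a full cohort's percentage, and they apply only where that subject was not already counted in the category. The analysis is descriptive and the sample size has no statistical basis, so no power or error rate is affected. It is a modest ascertainment gap in the primary endpoint and is worth closing because it is cheap to close.

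**What to change.** Reconcile Section 4.3.2, Section 7.4 and the early-discontinuation footnotes of Tables 1 to 3, and carry the change into SAP Appendix A:

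- Keep a prompt early-termination assessment for every subject withdrawn after dosing.
- Tie the EOS/Follow-up visit for withdrawn subjects to the interval after the last dose that the protocol already uses for completers.
- State in Section 7.4 that collection of new adverse events for withdrawn subjects runs to that same point.
- While editing, align Section 3.3, which requires the EOS procedures, with Section 4.3.2, which asks only for attempts.

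The cost is protocol wording and at most one extra assessment per withdrawn subject, since the outpatient follow-up visit is already in the schedule. Some withdrawn subjects may not return; for them the prompt assessment stands as the last observation, so nothing now collected is lost.

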## 4.4. Lifestyle and/or Dietary Requirements

- Subjects will be prohibited from consuming food or beverages containing grapefruit and/or pomelo for 14 days prior to the first study drug administration and during the study.
- Subjects will be prohibited from consuming alcohol for 48 hours prior to each admission to the CRU until discharge. Throughout the study, in case of any doubt about alcohol consumption, a test for alcohol may be performed if requested by an Investigator
- Subjects will be prohibited from consuming food or beverages containing xanthines (i.e., tea, coffee, cola drinks, energy drinks or chocolate) for 48 hours prior to each admission to the CRU until last discharge.
- Subjects will eat only the food provided by the CRU during confinement.
- Female subjects of childbearing potential will have to take appropriate measures to prevent pregnancy from at least 30 days prior to the first study drug administration,

Altasciences Project Number: CNO-P5-319

during the study and for at least 90 days after the last dose of the study drug, as described in Section 4.1. It is the participant's responsibility to notify the CRU if a pregnancy occurs from the end of their study participation until 90 days after the last dose of the study drug.

- Male subjects will be expected to use an acceptable contraceptive regimen and not to donate sperm from the first admission to the CRU, during the study, and until at least 90 days after the last study drug administration, as described in Section 4.1. Reporting for pregnancy in female partners is detailed in Section 7.5.
- For the Smoker cohorts, subjects will abstain from smoking tobacco cigarettes for at least 1 hour before and 2 hours after study drug administration. Subjects will also abstain from using nicotine-containing products other than tobacco cigarettes (e.g., pipes, cigars, e-cigarettes or vapes, nicotine topical patches, nicotine gum, or nicotine lozenges) or other tobacco products (cigars, cigarillos, pipes) during the study.

### 4.5. Concomitant Treatment

Except for medication which may be required to treat AEs, no other treatment or medication other than the study drugs will be allowed from the first dosing until all study activities and evaluations have been completed.

Systemic contraceptives and hormone replacement therapy are permitted for female subjects as per Section 4.1.

Subjects will be instructed to notify the CRU about any new medications taken after the start of the study treatment. All medications and significant non-drug therapies (including physical therapy and blood transfusions) administered after the subject has received the study treatment must be listed in the subject case report form (CRF). The drug name and dose taken will be noted. An investigator or delegate and/or the Sponsor will decide whether the subject will be permitted to remain in the study, depending on the drug used, the time of drug intake, etc.

Subjects receiving the COVID-19 vaccine should be fully vaccinated at least 14 days prior to receiving Investigational Product.

Altasciences Project Number: CNO-P5-319

#### 5. STUDY TREATMENTS

# 5.1. Investigational Products

All IPs will be provided by the Sponsor. The lot number and the measured content of the dosage form, if available, will be included in the final report.

#### 5.1.1. SBP-9330

SBP-9330 75 mg, 150 mg, and 300 mg capsules are manufactured by PACE Laboratory (previously Velesco Pharmaceutical Services, Inc.) for oral administration. Small batches of 75 mg dose strength capsules will also be prepared by the Altasciences pharmacy using a Sponsor-supplied procedure. Each white gelatin capsule contains SBP-9330 sodium equivalent to 75 mg, 150 mg or 300 mg SBP-9330.

#### 5.1.2. Placebo

Placebo capsules matched to Sponsor's SBP-9330 75, 150 and 300 mg capsules will be supplied by the Sponsor. The placebo formulation will be comprised of the same white gelatin capsule, filled with Avicel microcrystalline cellulose, without SBP-9330 (active ingredient).

## 5.2. Investigational Product Management

### 5.2.1. Packaging, Labeling and Dispensing

The Sponsor will be responsible for ensuring that the IP is manufactured in accordance with applicable current Good Manufacturing Practice regulations and requirements.

The IPs will be labeled according to the requirements of local law and legislation. The IPs will be dispensed by the CRU's pharmacy.

## 5.2.2. Storage and Handling

All study drugs will be shipped from the Sponsor or Sponsor resources to the CRU's pharmacy.

The study medication must be carefully maintained at 25°C; excursions permitted to 15-30°C.

The CRU's pharmacy will maintain an inventory record of the IPs received, stored (in a secure restricted area), and dispensed. IPs will be provided to study subjects only.

